## 2. Objectives

The specific aims and goals of this study include:

**Aim 1 (Phase 1-Year 1):** Describe the symptom trajectory and burden from the perspectives of patients, family caregivers, health professionals and other key stakeholders and collectively develop a symptom management toolkit.

*Goal 1:* Develop symptom management toolkit

**Aim 2 (Phase 2-Year 2):** Refine and pilot test the nurse-driven symptom management toolkit/intervention to decrease the symptom burden and increase the QOL of critically ill adults with multimorbidity.

*Goal 2:* Toolkit refinement/Intervention development

*Goal 3:* Intervention pilot test

*Goal 4: Intervention evaluation*

- Primary outcomes: Symptom burden, Quality of life
- Secondary outcomes: Pain, Fatigue, Social support, Resilience, Health-care utilization

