### **4. Study Procedures**

The proposed mixed method study will be conducted in two phases using social (justice)/human centered design. The first phase (Year 1) will empirically describe the prevalence and burden of symptoms from the perspective of patients, family caregivers, health professionals and other stakeholders. Using participatory co-design methodology, EBCD, we will develop a symptom

management toolkit. This approach will identify care delivery and care transitioning preferences and needs of patients with multimorbidity, family caregivers, healthcare providers, and other stakeholders. In the second phase, (Year 2) the data from phase one will inform the refinement and evaluation of a patient-centered symptom management intervention using a pre-post quasi-experimental design.

**Phase 1:** A collaborative study will be implemented to describe the symptom trajectory and burden including pain and fatigue and develop symptom management toolkit for critically ill adults with multimorbidity.

*Year 1, Goal 1:* Develop multimorbidity management (which includes symptom management) toolkit, using co-design, by understanding disease trajectories, symptom trajectory, burden, gender roles and needs of the patient and family caregivers and key stakeholders' priorities. To achieve goal 1 we will use the EBCD and follow its six-stage process (Table 1), using online EBCD toolkit for consistency in documentation and processes. We will work with patients, family caregivers, healthcare providers, and other stakeholders through iterative rounds of data collection, analysis, validation and development strategies to address symptom burden. EBCD takes typically 9-12 months to complete and is proven means for understanding how to make the best use of data about patient, family, and healthcare providers' experience to improve the quality of care and culture of health services. Table 1 details the activities required for each stage of the EBCD process.

[figure not shown]

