**Figure 2: Study protocol for Phase 2**

**Table 2: Phase 2**

Goal 2-4: Develop, pilot test and evaluate the toolkit/intervention	
Stages/Goals	Goals and Activities
Goal 2	Toolkit refinement/Intervention development Co-designed strategies/toolkit from phase 1 will be compiled in the user-friendly intervention protocol for implementation
Goal 3	Intervention pilot test Recruitment of 25 participants meeting eligibility criteria Baseline survey data collection on the same measures used in Phase 1, Stage 2 Initiation of co-designed symptom-management intervention pre-discharge with telephone follow-up (symptom burden will be assessed at each follow-up) Survey data collection, at the end of the intervention (i.e., 6 weeks) and at 3 months after completion of the intervention
Goal 4	Intervention evaluation Participants survey and interview on satisfaction, feasibility, and acceptability of the intervention Data analysis
Dissemination	Manuscripts and project summary Dissemination at professional organization R01 Randomized Control Trial planning for scalability of the intervention

*Year 2 Goal 2:* The user-friendly intervention protocol will be developed by refining the symptom management toolkit established in Phase 1. The intervention will be nurse-driven person-centered pre-discharge intervention engaging caregivers followed by telephone support, which will focus on the management of symptoms such as difficulty breathing, pain, fatigue and sleep disturbances among critically ill patients with multimorbidity and as identified from the survey on symptom burden.

*Year 2 Goal 3:* We will pilot test the intervention among 25 participants over 9 month's local rollout period. The symptom management intervention will be delivered by a nurse pre-discharge with telephone follow up over a 6 weeks period (at 48 hrs, 1 week, 4 weeks and 6 weeks) after the discharge from JHH-IMCU.

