*Year 2 Goal 4:* We will evaluate the effectiveness of the intervention on primary outcomes (i.e., symptom burden and QOL) by comparing pre-post intervention data (i.e., baseline, 6 weeks and 3 months). Additionally, the intervention is anticipated to improve secondary outcomes (i.e., pain, fatigue, social support, resilience, and healthcare utilization). To evaluate the acceptability and feasibility of the intervention both quantitative (survey items on satisfaction and acceptability, no. of nurse-patient contacts, recruitment rate and retention rate) and qualitative (unstructured interview with selected participants who attended the intervention and the nurse delivering the intervention) data will be examined.

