# Statistical Analysis Plan

- a. Primary outcome variable.
  - Symptom Burden: Edmonton Symptom Assessment System (ESAS)
  - Quality of Life: BRICS NINR Short Form Survey (SF-36)
- b. Secondary outcome variables.
  - Health-care Utilization: No. of emergency visit, Hospitalizations, Critical care admissions
- c. Statistical plan including sample size justification and interim data analysis.

Data collection and analysis are iterative processes throughout Goal 1, Stages 1-6 of the EBCD process, and Goal 3 and Goal 4 for intervention evaluation. The majority of data collected in phase 1, except the baseline survey, are qualitative and will be analyzed using thematic analysis. The software Atlas ti. will support qualitative analysis.

Quantitative data will be analyzed using descriptive statistics followed by inferential statistics. As a pilot study, the analyses of Phase 2 data will likely not have adequate power to detect significant differences. Therefore, effect sizes, followed by statistical significance will be explored for evidence of the effectiveness of the intervention on outcomes. To compare quantitative data at different time points, we will use Wilcoxon signed rank test to evaluate changes from baseline to 6 weeks and baseline to 3 months post-intervention. Additionally, the changes across baseline, 6 weeks, and 3 months post-intervention will be analyzed using the Friedman test for repeated measures, with Kendall's W employed to assess effect size.

Quantitative analyses will be performed using the Statistical Package for the Social Sciences (SPSS) or equivalent software. We will evaluate the acceptability and feasibility of the intervention using qualitative analysis of interview data from selected participants who attended the intervention, left the intervention if agree to interviewed and the nurse delivering the intervention. The quantitative data from satisfaction and feasibility items will be descriptively analyzed (mean, range, percentages). Further, evaluation of participants' recruitment rate, retention rate and no. of nurse patient interaction will be performed.

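### The SAP puts effect sizes ahead of significance but names only Kendall's W, which has no direction; neither Wilcoxon contrast has a signed estimate or confidence interval

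*Combined protocol and SAP*

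**What the plan says.** Aim 2 in section 2 (Objectives) has a direction: the intervention is meant "to decrease the symptom burden and increase the QOL of critically ill adults with multimorbidity". Section 4, Year 2 Goal 4, says how this will be judged: "We will evaluate the effectiveness of the intervention on primary outcomes (i.e., symptom burden and QOL) by comparing pre-post intervention data".

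Section c of the Statistical Analysis Plan accepts that the pilot will probably be underpowered and draws a consequence: "effect sizes, followed by statistical significance will be explored for evidence of the effectiveness of the intervention on outcomes". It then sets out three layers of analysis:

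- **Descriptive.** "Quantitative data will be analyzed using descriptive statistics followed by inferential statistics". The summaries are itemised (mean, range, percentages) only for the satisfaction and feasibility items, not for the outcomes.
- **Pairwise.** "we will use Wilcoxon signed rank test to evaluate changes from baseline to 6 weeks and baseline to 3 months post-intervention". No effect size, estimate of change or interval is attached.
- **Omnibus.** A Friedman test across the three visits, with Kendall's "W employed to assess effect size".

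No other effect size is named, and no confidence interval is mentioned anywhere in the protocol or SAP.

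**The concern.** The plan makes effect sizes its lead evidence, yet the only one it names cannot answer the question in Aim 2. W measures how consistently participants rank the three visits. It does not say which visit was better, it is not in ESAS or SF-36 points, and it is one figure across three visits, so it describes neither baseline contrast.

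If W is reported as planned, a reader learns that scores differed across visits but not whether patients got better, by how much, or whether a gain at 6 weeks lasted. The Wilcoxon tests add p-values, which the plan itself ranks second. What is missing is the size of change on each contrast with its uncertainty. That is the most useful outcome result a pilot of 25 can give, and the protocol lists "R01 Randomized Control Trial planning for scalability of the intervention" among its next steps.

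**Working it through.** **Inputs.** From the documents: n = 25 (Table 2, Goal 3) and k = 3 visits (SAP, section c). The documents give no SD, correlation, target effect, alpha or dropout rate, so the plan has no figure of its own to reproduce. The following are assumptions for illustration: normal scores, equal correlation r between visits (0 to 0.7), a shift of 0.6 raw-score SD, and 18 completers (or 20 or 15) in place of 25.

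**1. W has no direction.** Let R_j be the rank sum of visit j and S the sum of (R_j - n(k+1)/2)². Then W = 12S / [n²(k³ - k)]. With n = 25 and k = 3, W = 12S / (625 × 24) = S/1250.

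- Reversing the sign of every score turns R_j into n(k+1) - R_j. Each deviation changes sign and its square does not, so S and W are unchanged.
- Relabelling the visits only reorders the terms of S.
- If all 25 patients improve steadily, the rank sums are 75, 50 and 25, so S = 625 + 0 + 625 = 1250 and W = 1. If all 25 worsen steadily, the rank sums are 25, 50 and 75, and W = 1 again.
- In one simulated data set of 25, W was 0.1456 (Friedman p = 0.026). It was identical after sign reversal and after swapping baseline with 3 months. The Hodges-Lehmann change from baseline to 6 weeks went from -0.45 to +0.45, and the rank-biserial correlation from -0.56 to +0.56.

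This step needs none of the assumptions above.

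**2. W is not zero when nothing changes.** W = χ²_F / [n(k - 1)], and χ²_F averages k - 1 under the null, so W averages 1/n. At n = 25 that is 1/25 = 0.040 (simulated 95th percentile 0.12). At an assumed 18 completers it is 1/18 = 0.056 (95th percentile 0.16).

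**3. Three clinical courses, one W.** Mean W at n = 25 with a shift of 0.6 raw SD (100,000 simulated trials per cell):

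| Assumed r | Sustained improvement | Sustained worsening | Improved at 6 weeks, lost by 3 months |
|---|---|---|---|
| 0 | 0.118 | 0.118 | 0.118 |
| 0.3 | 0.148 | 0.148 | 0.148 |
| 0.5 | 0.187 | 0.187 | 0.186 |
| 0.7 | 0.267 | 0.267 | 0.267 |

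The same raw shift also gives a different W as r changes, so W alone does not give the size of the change in scale points.

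**4. What a signed estimate shows.** Hodges-Lehmann paired change with exact signed-rank 95% CI, averaged over 1,500 trials at r = 0.5, in raw-score SD (negative = lower symptom burden):

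| Course | Baseline to 6 weeks | Baseline to 3 months |
|---|---|---|
| Improvement | -0.59 (-1.01 to -0.17) | -0.60 (-1.02 to -0.18) |
| Worsening | +0.60 (0.18 to 1.02) | +0.60 (0.18 to 1.02) |
| Relapse | -0.60 (-1.02 to -0.18) | 0.01 (-0.42 to 0.43) |

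**5. Precision available.** The simulated half-width of this interval at n = 25 is about 0.42 SD of the change; the t formula gives 2.064/√25 = 0.41. The SD of change is √(2(1 - r)) raw SD, that is 1.41, 1.18, 1.00 and 0.77 for r = 0, 0.3, 0.5 and 0.7. Multiplying by 0.424 gives half-widths of about 0.60, 0.50, 0.42 and 0.33 raw SD. With fewer completers the half-width is about 0.49 SD of the change at n = 20 and 0.58 at n = 15.

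**The case against.** The best defence is that direction and size are largely covered already. Descriptive statistics are promised, and for participants seen at both visits the difference between visit means is the mean paired change in scale points. In 2,000 simulated trials at r = 0.5 with the 0.6 SD shift, that difference averaged -0.60 and had the right sign in 99.9%. Wilcoxon rank sums also show direction. The SAP speaks of effect sizes in the plural and nowhere makes W the measure for the Wilcoxon contrasts; W is the usual companion to Friedman. On this view the gap is a reporting detail in an exploratory, uncontrolled pilot.

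Much of this is fair. Direction would be recoverable, and the tests are valid. But the outcome summaries are not specified, visit means do not carry the uncertainty of the paired change, and an unnamed measure can be chosen after the data are seen. That matters when effect sizes are the lead evidence.

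Four narrower points also stand:

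- The equal W values in the table are true by construction, because the three courses are sign or label rearrangements of one another. They illustrate the invariance and do not add to it. Other shapes give other values, for example 0.154 for a gradual change (0, -0.3, -0.6) at r = 0.5.
- The 0.6 SD shift is not a low-power case: the Wilcoxon test rejected in about 81% of trials at r = 0.5.
- Hodges-Lehmann estimates a pseudomedian, which equals the median change only if the differences are symmetric.
- Without a control group, an interval for the change is not an interval for the intervention effect.

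None of these alters the conclusion.

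**Conclusion.** The point holds. The SAP gives first place to effect sizes and then names only one that cannot show whether symptom burden fell or quality of life rose. Neither Wilcoxon contrast has an estimate or interval. That W has no direction follows from its formula and rests on no assumption.

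The sizes shown (W of about 0.12 to 0.27 whichever way patients move, and CI half-widths of about 0.33 to 0.60 raw SD at n = 25) depend on the assumed shift and range of correlation, and on normal, untied scores. They illustrate the problem and do not forecast this trial's results.

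This should be changed, but it does not invalidate the analysis: the tests can stand, W can stay, and the data to be collected are sufficient.

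**What to change.** In section c of the SAP:

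1. For each primary outcome and each baseline contrast (6 weeks, 3 months post-intervention), name as lead effect measure a signed paired change in scale points with a 95% CI. The Hodges-Lehmann estimate pairs naturally with the Wilcoxon test. Say which ESAS and SF-36 score it applies to, since section a names only the instruments, and which sign means improvement.
2. Keep W as a descriptive companion to the Friedman test. A matched-pairs rank-biserial correlation is optional.
3. Report the mean and SD of change and the baseline-to-follow-up correlation. These would help plan the later randomised trial; the documents do not say that W would be used to size it.
4. State that, because section 4 describes "evaluation of a patient-centered symptom management intervention using a pre-post quasi-experimental design" with no control group, the signed change includes natural recovery after discharge.

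The cost is SAP wording and a few more rows in the results table. Participants, visits and data stay the same.
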